In a current, ongoing study (INCB 24360-202), enrollment is complete in the Phase 1 cohorts of epacadostat 25 mg BID, 50 mg BID, 100 mg BID, and 300 mg BID cohorts with pembrolizumab 2 mg/kg or 200 mg IV every 3 weeks (Q3W). The Phase 2 part of the study is still ongoing, in which the recommended Phase 2 dose (RP2D) of epacadostat 100 mg BID is being evaluated in combination with the fixed dose of pembrolizumab 200 mg IV Q3W. As of 28 MAR 2016, a total of 181 subjects have been enrolled to the study (both Phase 1 and Phase 2). Among the 117 subjects who have received epacadostat 100 mg BID in combination with pembrolizumab, the most frequently reported (> 15%) AEs of any grade for all treatment groups combined were fatigue (35.0%), constipation (24.8%), diarrhea (20.5%), nausea (20.5%), vomiting (18.8%), pyrexia (16.2%), and dyspnea (15.4%). Fatigue (13.7%) and rash (11.1%; including the preferred terms rash, rash maculopapular, rash generalized, and rash macular) were the only treatment-related AEs reported in > 10% of subjects. Treatment-related AEs of rash were only reported in the Phase 2 group.

The ORR in 19 evaluable subjects with treatment-naive metastatic melanoma was 53% (10/19), with disease control rate of 74% (14/19). Median progression-free survival (PFS) has not been reached, and all responses are ongoing with minimum follow-up of 31.7 weeks. Objective responses were also seen in other tumor types enrolled in Phase 1 ([Gangadhar et al2015](#)). Based off of data in Study INCB 24360-202, a Phase 3 study of epacadostat in combination with pembrolizumab has been initiated in subjects with unresectable or metastatic melanoma.

Refer to the epacadostat Investigator's Brochure ([IB](#)) for additional preclinical and clinical study data.

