Phase 1 studies of anti-PD-1 agents have demonstrated promising results. In 2015, the FDA granted approval for both pembrolizumab and nivolumab for the treatment of metastatic NSCLC after progression on or after platinum-based chemotherapy. Pembrolizumab was approved for patients whose tumors express PD-L1 as determined by an FDA-approved test and who have disease progression on or after platinum-containing regimens (Garon et al2015). Patients with EGFR or ALK genomic tumor aberrations should have disease progression on an FDA-approved therapy for these aberrations before receiving pembrolizumab. In the Phase 1 study by Garon et al (2015), an ORR of 19.4% was reported in the 495 NSCLC patients who received monotherapy pembrolizumab. Median DOR was 12.5 months, median PFS was 3.7 months, and OS was 12 months. Nivolumab was also approved in 2015 for patients with metastatic NSCLC with progression on or after platinum-based chemotherapy. Patients with EGFR or ALK genomic tumor aberrations should also have disease progression on an FDA-approved therapy for these agents. The Phase 3 study comparing nivolumab to docetaxel resulted in an OS of 12.2 months (95% confidence interval [CI], 9.7 to 15.0) among 292 subjects in the nivolumab group and 9.4 months among the 290 subjects in the docetaxel group (hazard ratio, 0.73; 96% CI, 0.59 to 0.89; $p = 0.002$). The response rate with nivolumab was 19% as compared with 12% in the docetaxel group ($p = 0.02$; Borghaei et al2015). Based on results in second-line advanced NSCLC, investigation of PD-1 pathway inhibitors moved to the first-line setting, evaluating PD-1-targeting antibodies as monotherapy as well as in combination with other immunotherapies and chemotherapy (Gettinger et al2016, Rizvi et al2016). On 05 AUG 2016, Bristol-Myers Squibb announced top-line results from the Phase 3 CheckMate-026 study evaluating nivolumab monotherapy versus investigator's choice chemotherapy in a first-line advanced NSCLC population. In the open-label, randomized study, nivolumab did not meet the primary endpoint of PFS in subjects with at least 5% PD-L1 expression on their tumors (Bristol-Myers Squibb 2016).

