Note: If a subject is scheduled to have a tumor biopsy for the purposes of this study, and it is subsequently determined that tumor tissue cannot be obtained, then the subject may still enroll in the study. [REDACTED]

Note: Care should be taken to biopsy the same lesion for the baseline and on-treatment samples. If a subject has a solitary target lesion, this should not be biopsied. [REDACTED]

4. Life expectancy >12 weeks.
5. ECOG performance status of 0 to 1.
6. Presence of measurable disease per RECIST v.1.1 as determined by the site study team. Tumor lesions situated in a previously irradiated area are considered measurable if progression has been demonstrated in such lesions. The lesion selected for pre- and/or post-treatment biopsy cannot be the only measurable lesion.
7. Willingness to avoid pregnancy or fathering children based on the criteria below:
 - a. Woman of nonchildbearing potential (ie, surgically sterile with a hysterectomy and/or bilateral oophorectomy OR 12 months of amenorrhea and at least 50 years of age.)
 - b. Woman of childbearing potential who has a negative serum pregnancy test at screening (must be performed within 72 hours before the first dose of study drug) and who agrees to take appropriate precautions to avoid pregnancy (with at least 99% certainty) from screening through 120 days after the last dose of study drug. Permitted methods that are at least 99% effective in preventing pregnancy (see [Appendix A](#)) should be communicated to the subject and their understanding confirmed.

- c. Man who agrees to take appropriate precautions to avoid fathering children (with at least 99% certainty) from screening through 120 days after the last dose of study drug. Permitted methods that are at least 99% effective in preventing pregnancy (see [Appendix A](#)) should be communicated to the subject and their understanding confirmed.

Part 1 Only

8. Subjects with histologically or cytologically confirmed advanced or metastatic solid tumors that have failed prior standard therapy (disease progression; subject refusal or intolerance is also allowable).

Note: There is no limit to the number of prior treatment regimens.

Part 2 Only

Note: Subjects must have failed available therapies that are known to confer clinical benefit as indicated below, unless they are ineligible, intolerant, or refused standard treatment.

Subjects with histologically or cytologically confirmed NSCLC:

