9.4.2. Secondary Analyses

Part 1: The proportion of subjects with advanced or metastatic solid tumors who meet the objective response criteria (CR + PR), as per RECIST v1.1, will be estimated with 95% CI.

Part 2: The clinical safety data (vital signs, ECGs, routine laboratory tests, and AEs) for subjects with previously treated Stage IV or recurrent NSCLC, Stage IV MSS CRC, and other select solid tumors will be summarized using descriptive statistics (eg, mean, frequency) using the safety population, which is detailed in Section 9.4.4.

Parts 1 and 2: The percentage of TIL responders for subjects with advanced or metastatic solid tumors and previously treated Stage IV or recurrent NSCLC and Stage IV MSS CRC will be estimated with 95% CI. A subject is considered a TIL responder if the subject has an increase in the number of TILs or the ratio of CD8+ lymphocytes to Tregs infiltrating tumor post-treatment versus pretreatment with pembrolizumab and epacadostat in combination with azacitidine, INCB057643, or INCB059872 evaluated by IHC.

Parts 1 and 2: PFS and DOR of subjects with advanced or metastatic solid tumors and previously treated Stage IV or recurrent NSCLC and Stage IV MSS CRC will be estimated using Kaplan-Meier method as per RECIST v1.1 if there are enough observations.

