2.3.1. Primary Endpoints

- Part 1: Safety and tolerability will be assessed by monitoring the frequency, duration, and severity of AEs; through physical examinations; by evaluating changes in vital signs and ECGs; and through clinical laboratory blood and urine sample evaluations.
- Part 2: Objective response rate, defined as the percentage of subjects having a CR or PR, will be determined by investigator assessment of radiographic disease as per RECIST v1.1.

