5.2. Treatment Groups

This is an open-label, multicenter, Phase 1/2 study evaluating the addition of an epigenetic priming regimen to an immunotherapy doublet in subjects with advanced or metastatic solid tumors. The study will be conducted in 2 parts.

Due to the stop of study enrollment, only subjects in Treatment Group A have been enrolled into Parts 1 and 2. Data from Parts 1 and 2 for Treatment Group A will be summarized together by dose level. The dose levels for Treatment Group A are shown in [Table 1](#).

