7.2.2. Objective Response Rates and Best Overall Response

A subject is defined as an objective responder if the subject has an overall response of CR or PR at any postbaseline visit prior to first PD. Objective responders will be assessed based on RECIST v1.1.

Objective response rate is defined as the proportion of subjects with objective responses. Objective response rate will be estimated with 95% CIs overall by cohort-specific tumor type. CIs will be calculated based on the method for Simon 2-stage CIs of response rates outlined in Koyama and Chen (2008). Subjects who do not have sufficient baseline data to ascertain response will be included in the denominators in the calculation of ORR.

In general, the best response is determined on subject level using the highest overall response achieved postbaseline prior to and including the first PD, in the order of CR, PR, SD, PD, and NE. Responses of CR, PR, or SD after a response of PD will not be considered in determining best response by RECIST v1.1 criteria. In the case of SD, measurements must meet the SD criteria at least after the date of first dose at a minimum of 56 days (9 weeks – 7-day window). Subjects who fail to meet this criterion will have best overall response of PD if the next available assessment indicated PD, or NE if there is no additional assessment available.

Under RECIST v1.1, the best response is determined by subject using the highest overall response achieved postbaseline prior to and including the first PD, in the order of CR, PR, SD, PD, and NE. Responses of CR, PR, or SD after a response of PD will not be considered in determining best response by RECIST v1.1 criteria. In the case of SD, measurements must meet the SD criteria at least after the date of first dose of study drug at a minimum of 56 days (9 weeks – 7-day window). Subjects who fail to meet this criterion will have best overall

response of PD if the next available assessment indicated PD, or NE if there is no additional assessment available.

For subjects with measurable disease at baseline, the RECIST v1.1 assessment criteria presented in [Table 11](#) can be used to determine the overall disease status at a given time point based on the target lesion, nontarget lesion, and new lesion assessment.

Table 11: RECIST Evaluation Criteria for Overall Response: Measurable Disease at Baseline

Target Lesions	Nontarget Lesions	New Lesions	Overall Response
CR	CR	No	CR
CR	Non-CR/Non-PD	No	PR
CR	NE	No	PR

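### The SAP's rule to summarize Parts 1 and 2 together by dose level has no exception for response, so the primary Part 2 ORR is not clearly estimated in its own population

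*SAP*

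**What the plan says.** The endpoints are specific to each part. SAP 2.3.1 gives the primary efficacy endpoint as "Part 2: Objective response rate, defined as the percentage of subjects having a CR or PR". SAP 2.3.2 and Protocol 9.4.2 make Part 1 ORR a secondary endpoint with its own estimate.

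SAP 5.2 then sets a general rule: "Data from Parts 1 and 2 for Treatment Group A will be summarized together by dose level". SAP 5.3.1 defines one response evaluable population drawn from everyone enrolled and assigns it to all RECIST-based response analyses. Table 2.1.1 in SAP Appendix A uses that population.

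The specific text on response is in SAP 7.2.2: "Objective response rate will be estimated with 95% CIs overall by cohort-specific tumor type". It adds that "CIs will be calculated based on the method for Simon 2-stage CIs of response rates outlined in" a cited paper on inference after two-stage designs. It does not mention Part 1 or Part 2.

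SAP 10.1, which lists departures from the protocol's analyses, does not include the pooling. SAP 9 and 10.1.3 record that, because the study ended early, neither the Simon design nor the Part 2 interim analysis will be carried out.

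**The concern.** Subjects in the two parts entered under different rules. Part 1 took "Subjects with histologically or cytologically confirmed advanced or metastatic solid tumors that have failed prior standard therapy" (Protocol 3.1, Part 1 criteria), with no requirement for PD-1 failure or MSS status. Cohort A-1 requires NSCLC that progressed while on a PD-1 pathway agent, and A-2 requires confirmed MSS colorectal cancer. Melanoma subjects in A-3 and A-4 must have progressed on a PD-1 agent, whereas A-5 takes only untreated melanoma.

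If the SAP 5.2 rule governs ORR, the reported rate is a mixture whose weights depend on who happened to enroll in Part 1 at the expansion dose. The protocol's primary quantity, response in the Part 2 cohorts, might then never appear as an estimate of its own. The interval in 7.2.2 assumes a single cohort sampled under a two-stage rule, so it would be attached to data that did not arise that way.

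**Working it through.** **1. The plan's design figures.** SAP Table 10 has p0 = 3%, p1 = 20%, n1 = 8, n = 27, r1 = 0, r = 2. The probability of stopping after Stage 1 is (1 − p)^8:
- at 3%: 0.97^8 = 0.7837
- at 20%: 0.80^8 = 0.1678

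Both match Protocol 9.6. The exact two-stage type I error is 0.0319 and the power is 0.8002, so the design is correctly stated. In Treatment Group A it covers A-1 and A-2 only. Part 1 and A-3 to A-5 have no two-stage design.

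**2. What the pooling rule does if applied to ORR.** Part 2 runs at the recommended dose carried forward from Part 1 (SAP 3.1.3.1). The dose-level group that holds A-1 to A-5 therefore also holds any Part 1 subjects treated at that dose. SAP 3.4.1.1 allows 3 to 9 subjects per dose level, of any tumor type. The number k sharing a tumor type with A-1 could be 0, or up to 9 if all were NSCLC.

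**3. Effect on the A-1 estimate.** Let n2 be the number of A-1 subjects, with a true rate of 3%, and q the response rate of the k added Part 1 subjects.

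Expected pooled ORR = (n2 × 0.03 + k × q) / (n2 + k)

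For q, 19.4% comes from Protocol 1.7.3.1 ("an ORR of 19.4% was reported in the 495 NSCLC patients who received monotherapy pembrolizumab"), and 35% is the pembrolizumab plus epacadostat rate in 40 NSCLC subjects in Protocol 1.7.3.3. The values 0% and 10% are assumptions, and so is every k. Final enrollment is not given, so n2 is shown at 27 (full cohort) and at 8 (Stage 1 only).

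| n2 | k | q = 0% | q = 10% | q = 19.4% | q = 35% |
|---|---|---|---|---|---|
| 27 | 3 | 2.7% | 3.7% | 4.6% | 6.2% |
| 27 | 9 | 2.3% | 4.8% | 7.1% | 11.0% |
| 8 | 3 | 2.2% | 4.9% | 7.5% | 11.7% |
| 8 | 9 | 1.4% | 6.7% | 11.7% | 19.9% |

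Examples: (27 × 0.03 + 9 × 0.35) / 36 = 3.96 / 36 = 11.0%; (8 × 0.03 + 3 × 0.194) / 11 = 0.822 / 11 = 7.5%. With k = 0 the value stays at 3.0%.

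**4. Melanoma, if tumor type is read across cohorts.** A-5 plans 10 first-line subjects. A-3 and A-4 plan 5 to 8 melanoma subjects each, so 10 to 16 PD-1 failures. Protocol 1.3 reports 53% (10 of 19) in treatment-naive melanoma on pembrolizumab plus epacadostat. The documents give no rate for PD-1-failure melanoma, so 3% is assumed.
- 10 failures: (10 × 0.53 + 10 × 0.03) / 20 = 28%
- 16 failures: (10 × 0.53 + 16 × 0.03) / 26 = 22%

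Neither value describes either group.

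**The case against.** The strongest reply is that the SAP does not actually order a pooled ORR. Where it clearly pools an analysis (SAP 6.1 to 6.2, and ECG abnormalities in 8.5), it repeats that Parts 1 and 2 are combined by dose level. That phrase is absent from the efficacy section. SAP 7.2.2 has its own rule by cohort-specific tumor type, and only the expansion cohorts have specified tumor types. On that reading A-5 is also kept apart from A-3 and A-4. Table 2.1.1 adds little either way, because Appendix A titles do not name a part even for tables the text expressly pools. Subject-level response listings are also planned. All of this stands, and it makes a pooled ORR one reading rather than an explicit instruction. It does not remove the conflict: 5.2 is unqualified, 7.2.2 does not exclude Part 1, and a programmer has no text saying which rule governs.

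Three stronger readings are tempting, and the documents do not support them.

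- **Inflated type I error against the 3% null.** If the cutoff of 3 responses in A-1 were still used, adding 3 to 9 Part 1 subjects with response rates of 10% to 35% would raise the false-positive probability from 0.032 to between 0.055 and 0.202. But SAP 9 and 10.1.3 drop the procedure, so there is no cutoff to cross. Type I error wording remains in SAP 3.3 and Table 10, but only as design-stage text. Nor is 3% solely a PD-1-failure benchmark; it is also the null for MSS CRC.
- **Part 1 responses were known before the Part 2 dose was chosen.** Group A dose decisions rest on toxicity through Day 21, while scans are every 9 weeks. The documents do not say which responses were known.
- **The bias must be upward.** Part 1 had no limit on prior regimens, and PD-1 agents were already approved in NSCLC, so some Part 1 NSCLC subjects may also have been PD-1 failures. The q = 0% column shows that pooling can lower the estimate.

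**Conclusion.** The point holds as an unresolved conflict within the SAP. The general pooling rule, the part-specific primary endpoint and the Simon-type interval cannot all apply to the same ORR. As written, the plan does not guarantee that the primary Part 2 ORR is estimated on Part 2 subjects alone. If the parts are pooled, the stated interval is invalid for the result.

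The consequence is possible bias in a descriptive estimate. In the A-1 illustration the expected value moves from 3.0% to somewhere between 1.4% and 19.9%, depending on assumed values of k, q and cohort size; it does not move at all if no Part 1 subject shares the tumor type and dose. Part 1 tumor-type counts, prior PD-1 exposure and final enrollment are not in the documents, so neither size nor direction can be settled. The correction should be made before the tables are produced, but it does not overturn any formal test.

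**What to change.** - **SAP 5.2:** limit the combined Part 1 and Part 2 summary to baseline, exposure and safety.
- **SAP 7.2.2 and Table 2.1.1:** report the primary ORR separately for each of A-1, A-2, A-3, A-4 and A-5, using only subjects enrolled in that cohort. Never combine first-line melanoma with PD-1-failure melanoma. Report Part 1 ORR by dose level as the secondary endpoint.
- **Confidence intervals:** do not attach the Simon two-stage interval to Part 1, to pooled data or to cohorts without a two-stage design. An exact binomial interval, which the statistical methods in the Protocol synopsis already mention, is suitable there.
- **SAP 10.1:** if a pooled ORR is kept, label it supplementary and list it as a departure from the protocol.

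The cost is SAP wording and some extra table columns. Each estimate rests on fewer subjects and its interval will be wider.

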5.3. Analysis Populations

5.3.1. Response Evaluable Population

The response evaluable population includes all subjects enrolled in the study who received at least 1 dose of study drug (epacadostat, pembrolizumab, or azacitidine), completed a baseline scan, and met at least 1 of the following criteria:

- The subject has ≥ 1 postbaseline scan.
- The subject has been on study for a minimum of 70 days of follow-up.
- The subject has discontinued from treatment.

All RECIST-based response analyses will be conducted using the response evaluable population.

5.3.2. Safety Population

The safety population includes all subjects enrolled in the study who received at least 1 dose of study drug (epacadostat, pembrolizumab, or azacitidine). All safety analyses will be conducted using the safety population.

Specific safety analysis populations to be used for study drug-specific tables include the following subgroups:

- Epacadostat safety population
- Pembrolizumab safety population
- Azacitidine safety population

6. BASELINE, EXPOSURE, AND DISPOSITION VARIABLES AND ANALYSES

[Appendix A](#) provides a list of planned tables and listings.

6.1. Baseline and Demographics, Physical Characteristics, and Disease History

6.1.1. Demographics

The following demographics will be summarized for the safety population by dose level for Treatment Group A in Parts 1 and 2 combined: age, sex, race, and ethnicity.

6.1.2. Baseline Disease Characteristics and Disease History

Primary diagnosis, TNM staging, stage at diagnosis, current stage, disease histology, and primary site of disease will be summarized for all subjects in the safety population by dose level for Treatment Group A in Parts 1 and 2 combined.

ECOG performance status will be summarized for all subjects in the safety population by dose level for Treatment Group A in Parts 1 and 2 combined.

6.1.3. Prior Therapy

Number of prior systemic cancer therapy regimens will be summarized for all subjects in the safety population by dose level for Treatment Group A in Parts 1 and 2 combined. Regimen name, component drugs, start and stop date, purpose of the regimen, best response, reason for discontinuation, and date of relapse/progression will be listed.

Number of subjects who received prior radiation will be summarized for all subjects in the safety population by dose level for Treatment Group A in Parts 1 and 2 combined. Radiotherapy type, body site, start and stop date, reason for regimen, number of fractions, total dose, and best response will be listed.

Number of subjects who had prior surgery or surgical procedure for the malignancies under study will be summarized for all subjects in the safety population by dose level for Treatment Group A in Parts 1 and 2 combined. Date and description of the surgery/procedure will be listed.

6.1.4. Medical History

Medical history will be summarized for all subjects in the safety population by dose level for Treatment Group A in Parts 1 and 2 combined. This summation will include the number and percentage of subjects with significant medical history for each body SOC as documented on the eCRF.

6.2. Disposition of Subjects

The number and percentage of subjects who entered the initial treatment phase, the initial follow-up phase, the re-treatment phase, and the re-treatment follow-up phase will be summarized. Under each phase (initial treatment phase and re-treatment phase), the number and percentage of subjects who discontinued study treatment with primary reason for discontinuation and withdrew from the study with a primary reason for study withdrawal will be summarized for all subjects in the safety population by dose level for Treatment Group A in Parts 1 and 2 combined. The number of subjects enrolled by site will also be provided for the safety population by dose level for Treatment Group A in Parts 1 and 2 combined.

6.3. Protocol Deviations and Violations

Protocol deviations and violations recorded on the eCRF will be presented in the subject data listings. If data warrant, protocol deviations and violations will be summarized descriptively.

6.4. Exposure

For subjects in the safety population, exposure to epacadostat, pembrolizumab, and azacitidine will be summarized descriptively.

6.4.1. Exposure for Epacadostat

Exposure for epacadostat will be summarized as follows:

- **Duration of treatment (days):** Date of last dose of epacadostat – date of first dose of epacadostat + 1.
- **Average daily dose (mg/day):** Total dose administered (mg) / duration of treatment (days).
- Number and percentage of subjects with 0 to 3, > 3, > 6, and > 9 months duration of exposure.

